7.3 Formal Definitions of Selected or Anticipated Adverse Events and Safety Outcomes

The outcomes and events defined below as adverse events are anticipated and will be closely tracked. The expected incidence data is based on events tracked in the THAPCA-OH Trial. Events tracked daily as primary safety outcomes in THAPCA-OH are indicated by an asterisk *. When applicable, some but not all of the tracked outcomes below would be serious adverse events. The below events are based on study defined definitions of these occurrences, as outlined in the MOP.

Selected or Anticipated Adverse Events and Safety Outcomes	Expected Incidence
*Pneumonia, Blood Stream Infection, or Urinary Tract Infection	39-46%
*Cardiac arrhythmias requiring intervention	9-11%
Neurological worsening	40-60%.
Hypokalemia	14-23%
Neutropenia	1-3%
Thrombocytopenia	1-10%
Seizures	35-41%
Repeat cardiac arrest	7-9%
*Any blood-product use	54%
Cryoprecipitate	8-9%
FFP	30-33%
PRBCs	42-43%
Platelets	9-12%

7.4 Unanticipated Problems

An Unanticipated Problem (UAP) generally includes any incident, experience or outcome that meets all of the following criteria: (1) Unexpected in terms of nature, severity or frequency, (2) related or possibly related to participation in the research and (3) suggests that the research places participants or others at a greater risk of harm (including physical, psychological, economic, or social harm) than was previously known or recognized. All UAPs will be reported to the IRB and/or FDA according to standard reporting guidelines.

8. TRAINING

The SIREN network utilizes multiple methods to optimize education and training of site personnel including both virtual and face-to-face training at investigator meetings employing audience interaction systems to identify comprehension of topics in real time, instantly remediate topics as required, and certify based on individual competency. Online training modules and certifications are also employed when appropriate for re-training or training of additional personnel.

At all P-ICECAP enrollment locations, the site principal investigator, study teams, treating physicians, inpatient nursing staff, and outcome assessment investigators will receive appropriate training prior to study initiation. There will be training meetings either virtually or in person annually including one meeting prior to any trial enrollment. Training decay will be minimized with scheduled recertification and/or refresher training of study and clinical staff. Personnel responsible for outcomes assessment will be recertified frequently to ensure inter-rater reliability.

Clinical principal investigators from the study leadership will evaluate each site prior to initiation to provide and assess adequacy of training and organization. Investigator and research coordinator meetings will occur monthly. In addition, P-ICECAP includes the following specific training programs:

Hypothermia administration: Approximately two-thirds of the study sites were former THAPCA trial sites that used a standardized protocol for therapeutic hypothermia temperature management for Induction, Maintenance, Rewarming and Normothermia phases. At training meetings to be conducted prior to the start of enrollment and then annually thereafter; a review of the physiology of cooling, target temperature management phases, and best practices will be conducted. The CCC will evaluate the existing protocols of study sites as part of site initiation. Additionally, as was done in the THAPCA trial, there will be 24/7/365 coverage by an experienced investigator to assist any site PI or bedside clinical team with questions related to cooling or the study protocol. For sites that did not participate in THAPCA, the site PI will contact the on-call study investigator at the time of enrollment and then daily through 120 hours for the first two enrollments. A daily review of the study protocol will be required with the on-call expert. Special emphasis related to the details of the rewarming period will be reviewed prior to each participant entering this phase of targeted temperature management. Note that in the THAPCA trials all sites were required to call the expert on call to discuss enrollment for the first two enrolled cases, so the P-ICECAP investigators have much experience in this real-time training.

Clinical standardization: A training program will teach the consensus standardization guidelines created for P-ICECAP to clinical care teams at participating sites to reduce variability in standard practice. Updated AHA guidelines on pediatric post arrest care by an expert group lead by one of the P-ICECAP PIs was recently published and will provide the framework (Topjian, 2019).

Outcomes assessment training: To address the need for certification in the patient reported outcome

measures, training will be done by the P-ICECAP Kennedy Krieger Institute outcome center and involve didactic and hands-on training with the tablet computer testing equipment.

Periodic investigator meetings: To address any impediments to participant enrollment, discrepancies in treatment between centers, and protocol violations of concern, we will hold meetings including investigators and site research staff. In addition, this will afford an opportunity to discuss any changes in the standard of care during the study period.

9. STATISTICAL CONSIDERATIONS

This trial will enroll a maximum of 900 participants. The primary outcome will be the “VABS-3 Mortality Composite Score” in which enrolled participants who die before the 12-month outcome are scored 0 and the age-adjusted standardized VABS-3 composite score is assigned for the survivors. The design of this trial is based on a statistical model of the mean VABS-3 Mortality Composite Score, i.e. the duration response curve. All participants will be receiving targeted temperature management at the time of enrollment as a condition of inclusion and will then be randomized to one of ten possible treatment arms for the duration of cooling. The ten possible treatment arms are 0, 12, 18, 24, 36, 48, 60, 72, 84, or 96-hours of cooling.

Participants will be adaptively randomized to a cooling duration, inclusive of a no additional cooling arm (controlled normothermia). The trial will determine the shortest duration of cooling that provides the maximal treatment effect and whether increasing durations of cooling are associated with better neurological outcomes. Regardless of whether participants are ever allocated to the no additional cooling arm (or have possible exposure to some pre-randomization cooling), an increasing treatment effect across some set of durations may imply a dose (duration) response effect. In this section we provide a detailed overview of the statistical design and operating characteristics. Further details are provided in the Statistical Analysis Plan (SAP).

9.1 Primary Endpoint

The VABS-3 ranges from 20 to 140 (mean age-corrected standardized score of 100) where higher scores indicate better cognitive outcomes. Deaths are assigned a score of 0. The VABS-3 Mortality Composite Score will analyze the combined deaths and survivors in a single analysis.

9.2 Primary Analysis

The primary analysis of the trial will model the mean VABS-3 Mortality Composite Score at 12 months for each treatment arm. The primary analysis is conducted on the intent to treat (ITT) population. The primary analysis will address two objectives: 1) to determine whether increasing durations of cooling are associated with better outcomes (Objective A); 2) identify the most likely target duration, where the target duration is the shortest duration that achieves the maximum treatment effect (Objective B). If increasing durations of cooling are

associated with an increasing treatment benefit in at least one part of the duration-response curve, then this may demonstrate a dose (duration) response effect in improving neurological outcomes.

9.3 Statistical Models

9.3.1 Duration-Response Curve Model

We model the mean 12-month VABS-3 Mortality Composite Score across the ten treatment arms with a duration-response model. All conclusions about each treatment arm will be based on a duration-response model. The duration response model restricts the shape of the duration response curve to have 3 phases – an increasing phase, a plateau phase, and a decreasing phase. We create a parametric family for this inverted-U duration response model.

Let Y_i be the primary composite outcome measured at 12 months for the i^{th} participant. We model the outcomes as

$$Y_i \sim N(\theta_{d_i}, \sigma^2)$$

where θ_d is the mean response for arm d .

The U-shaped dose-response model allows for an initial increase in the mean with dose, followed by a leveling out of the mean, then a decrease. The dose-response curve can be characterized in four different regions of the dose space:

$$\theta_0 = \begin{cases} \theta_0 + \delta \left(\frac{d}{p_{min}} \right)^\alpha & 0 < d < p_{min} \\ \theta_0 + \delta & p_{min} < d < p_{min} + p_{width} \\ \theta_0 + \delta \left(1 - \frac{d - (p_{min} + p_{width})}{w_{width}} \right)^\beta & p_{min} + p_{width} < d < p_{min} + p_{width} + w_{width} \\ \theta_0 & d > p_{min} + p_{width} + w_{width} \end{cases}$$

where d corresponds to the duration of cooling index (1 through 10). For the lowest dose region near 0 hours ($d = 1$), the dose-response curve is modeled as (potentially) increasing. The next region is the plateau, where the dose-response curve is assumed constant. For the third region, the dose-response curve is decreasing. For the final region, the dose-response curve is again constant, at the same level as the zero-dose. Since some participants will be cool prior to randomization, the controlled normothermia arm is considered to be longer than zero in the above equation.

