1.2 Secondary Objectives

The secondary objectives of this project are:

- i. To characterize the effect of duration of cooling on a global function measure, the Pediatric Cerebral Performance Category (PCPC).
- ii. To characterize the effect on a standardized neurological outcome measure, the Pediatric Resuscitation after Cardiac Arrest (PRCA) score
- iii. To characterize the overall safety and adverse events associated with duration of cooling
- iv. To characterize mortality of varying durations of cooling
- v. To determine if age group, etiology of CA, or initial GCS motor score influence primary outcome
- vi. To characterize the effect of cooling on family reported quality of life

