4.2 Exclusion Criteria and Rationale

Criteria

Exclusion Criteria

- Glasgow Coma Motor Score (GCMS) = 6
- LAR does not speak English or Spanish
- Duration of CPR > 60 minutes
- Severe hemodynamic instability requiring continuous infusion of epinephrine or norepinephrine of 2 µg/kg/minute or initiation of ECMO
- Pre-existing severe neurodevelopmental deficits with PCPC =5 or progressive degenerative encephalopathy
- Pre-existing terminal illness, unlikely to survive to one year
- Cardiac arrest associated with brain, thoracic, or abdominal trauma
- Active and refractory severe bleeding prior to randomization
- Extensive burns or skin lesions incompatible with surface cooling
- Planned early withdrawal of life support before 120 hours
- Sickle cell anemia
- Pre-existing cryoglobulinemia
- Non-fatal drowning in ice covered water
- Central nervous system tumor with ongoing chemotherapy
- Previous enrollment in P-ICECAP trial
- Prisoner
- Chronic hypothermia
- New post-cardiac arrest diabetes insipidus
- Pregnancy

Rationale for selected eligibility criteria - Exclusions:

Participants with GCMS of 6 lack evidence of brain injury and are outside the scope of this trial.

Legally authorized representative (LAR) does not speak English or Spanish is excluded because the VABS-3 is not available in other languages.

Participants with OHCA CPR duration of >60 minutes are expected to have profound brain injury and may not benefit from hypothermia.

Severe hemodynamic insufficiency requiring high vasoactive doses or ECMO and/or ECMO during CPR to achieve return of circulation for OHCA is associated with very high mortality and is not offered at many hospitals.

Several pre-existing conditions may confound the outcome determination. Examples include participants with severe baseline neurodevelopmental deficits (PCPC =5) would likely not have measurable changes in VABS-3 except for death.

A progressive, degenerative encephalopathy may lead to worsening by the time the primary outcome is assessed independent of the intervention.

Patients with preexisting terminal conditions would not be able to contribute outcome data if they are not expected to survive to the one year neurological outcome assessment.

Severe trauma raises concern for exacerbating hemorrhage. Cooling for treatment of severe head trauma has been studied previously and had no benefit on patient outcome.

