4.3 Study Enrollment Procedures

The on-call P-ICECAP study team will respond to the PICU clinical team’s notification to screen survivors of OHCA for eligibility, engage eligible patient’s LAR in an informed consent process, coordinate with the clinical care team, and randomize eligible participants. Enrollment case report forms will be completed in the PICU, where the study teams will determine and identify the sources for the times of arrest. Of note, this is routine information obtained by transport teams, pediatric emergency medicine specialists, and pediatric intensivists who care for children after OHCA.

The study team will follow each enrolled participant daily until day 10 for data collection and shepherding of clinical standardization through ICU stay. There is additional data collection at hospital discharge, and the follow up assessments at 3 and 12 months. P-ICECAP will use strategies described in THAPCA-OH that achieved a 98% one-year follow-up success rate (Gildea, 2020).

A screen log that includes all patients with a PICU diagnosis consistent with OHCA (ICD-10 code of I-46, I-46.2, I-46.8, I-46.9, I-49.01, I47.2, R95, R96, R98, R99, or equivalent codes in another diagnostic system) that are treated in the PICU but not enrolled will be completed at all sites.

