9.3.2 Longitudinal Model of 12-month VABS-3 Mortality Composite Score

At each interim analysis there will be participants who have not yet reached 12-months and will therefore not have a final outcome. We use the 3-month VABS-3 Mortality Composite Score as possibly predictive of the 12-month score, allowing participants with this earlier measurement to be included in the analyses of the 12-month measurement. This modeling is referred to as the longitudinal model. The longitudinal model allows for learning the relationship between the 3-month and 12-month VABS-3 Mortality Composite Scores as the accruing empirical data is used to determine the strength of the association between the two values. The observed 12-month values are augmented by multiple imputations from the longitudinal model (simple linear regression) for participants with an unknown 12-month value.

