9.9 Subgroup Analyses

Further details of the pre-planned secondary analyses will be available in the full SAP. Analyses for important subgroups (gender, age strata, ethnicity/race, baseline PCPC, mechanism of injury, witnessed arrest, duration of chest compressions) will be conducted for the primary endpoint and secondary endpoints identified in the SAP.

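### Low-severity improvement: the primary model in 9.3.1 has no baseline covariate, so a modest gain in precision from data the trial already needs is left unused

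*Protocol*

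**What the plan says.** Section 9.3.1 of the protocol introduces the primary model with "We model the mean 12-month VABS-3 Mortality Composite Score across the ten treatment arms with a duration-response model". It then writes the likelihood: each 12-month score is normal around theta_d with a single variance, where theta_d "is the mean response for arm d" and depends on the duration index only. The section rests every conclusion about an arm on this model. The one other regression, in 9.3.2, fills in unknown 12-month scores by "multiple imputations from the longitudinal model (simple linear regression") on the 3-month score, which is a post-randomization value.

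Baseline variables appear in several other places:

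- Secondary objective v (1.2): "To determine if age group, etiology of CA, or initial GCS motor score influence primary outcome".
- Subgroup factors (9.9) include "mechanism of injury, witnessed arrest, duration of chest compressions".
- Eligibility (4.2) excludes "Duration of CPR > 60 minutes" and "Glasgow Coma Motor Score (GCMS) = 6", so CPR time and motor score are assessed before randomization. On the enrollment forms (4.3), "the study teams will determine and identify the sources for the times of arrest".
- Pre-arrest PCPC is used to check balance between groups (6.1), and the change in PCPC from baseline to 12 months is evaluated (6.3).

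Section 4.5 gives the avoidance of chance imbalance in prognostic factors as one aim of randomization. Section 10.4 describes allocation from the current randomization vector and names no stratification factor. The protocol nowhere mentions covariate adjustment of the primary analysis.

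**The concern.** Deaths score 0, so much of the spread in the composite is death against survival. A pre-randomization variable that predicts survival would take some of that spread out of the residual variance. The same fitted model yields the duration-response curve, the allocation probabilities and both primary objectives, so lower residual variance would help all of them. No baseline VABS-3 is obtained (6.1), so patient and arrest characteristics are the main source of such precision. Section 4.5 also attaches importance to prognostic balance, yet the protocol text provides for it neither through a named stratification factor nor through a model term.

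What is at stake is efficiency. An unadjusted comparison of randomized arms is a legitimate primary analysis. Because the likelihood is printed in the protocol, this is a comment on a stated choice and not on detail left to the SAP.

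**Working it through.** **1. The plan's own figures.** In Table 9.7.A, composite mean = survival × mean VABS-3 among survivors: 0.45 × 65 = 29.25 (stated 29.3) and 0.55 × 75 = 41.25 (stated 41.3). In Table 9.7.B, early + late efficacy = overall power: 3.8 + 88.5 = 92.3 for the planning scenario (Plateau at 72 hours). The 92.3% itself cannot be recomputed, because the protocol does not give the survivor SD, the priors, the final success threshold or the realized allocation. Section 9.7 says that closed formulas are not available for this design.

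**2. How much of the variance is survival.** Null row: variance = 0.45 × SD² + 0.45 × 0.55 × 65². The second term is 1,045.7. The survivor SD is assumed:

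| SD | Variance | Share due to death v survival |
|---|---|---|
| 15 | 1,147 | 91% |
| 20 | 1,226 | 85% |
| 25 | 1,327 | 79% |

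**3. What a given R² would require.** For a half-and-half baseline split that shifts survival by ±d, R² = (65d)² / variance. At SD 20, d = √(R² × 1,226) / 65:

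- R² 2%: d = 0.076, survival 37% v 53%
- R² 5%: d = 0.120, survival 33% v 57%
- R² 10%: d = 0.170, survival 28% v 62%

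**4. Effect on power.** Assumptions: the stated 4.6% error is one-sided (z = 1.685), and R² is 2, 5 or 10%. Non-centrality = z(power) + 1.685, which is then divided by √(1 − R²) and converted back.

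Planning scenario: 1.4255 + 1.685 = 3.110. At R² 5%, 3.110 / 0.9747 = 3.191, and Φ(3.191 − 1.685) = 93.4%.

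| Scenario | Stated | R² 2% | R² 5% | R² 10% |
|---|---|---|---|---|
| Plateau at 72 h | 92.3 | 92.7 | 93.4 | 94.5 |
| Plateau at 48 h | 89.7 | 90.2 | 91.0 | 92.3 |
| Constant upslope | 90.9 | 91.4 | 92.1 | 93.3 |
| U-shaped (upper bound) | 66.5 | 67.3 | 68.5 | 70.6 |

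Equivalent N = 900 / (1 − R²) = 918, 947 and 1,000. Standard errors fall by 1 − √(1 − R²) = 1.0, 2.5 and 5.1%. Reading 4.6% as two-sided gives 92.8, 93.5 and 94.6% for the planning scenario and 67.4, 68.8 and 71.1% for the U-shape, a change of about half a point at most. The U-shaped row is an upper bound because curve shape and allocation may limit power there as well as variance.

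**5. Check of the algebra.** A simplified simulation with the death-at-zero outcome (ten equal fixed arms, linear trend, N = 790, 20,000 runs) gave 92.4–92.6% unadjusted, 93.7% at R² 5% and 94.5% at 10%, with null rejection of 4.5–4.8%. This is not the trial's design. A rough imitation of the adaptive rules, with assumed priors and an assumed final criterion, gave 57% where the plan states 92.3%. It is not a usable stand-in, and no adaptive figure is claimed.

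**The case against.** The strongest reply is that nothing here is wrong. The unadjusted model is valid, its operating characteristics were simulated, and power is about 90% or more in every effective scenario except the U-shape. That stands, and it fixes the point as a suggestion. The related argument, that covariates belong in the SAP, is weaker: section 9.3.1 prints the likelihood, so a SAP that added terms would change it.

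The size of the gain is also open to challenge. No R² is documented, and objective v treats the influence of these variables as an open question. Excluding long CPR and a motor score of 6 narrows the range of two predictors, and VABS-3 is already age-standardized. An R² of 10% would need a strong split (28% v 62% survival). At R² 2% the planning-scenario gain of about 0.4 points lies within simulation noise: with 10,000 runs the Monte Carlo standard error of 92.3% is √(0.923 × 0.077 / 10,000) = 0.27 points. All of this stands.

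Two stronger readings are tempting. A reader might infer that adjustment would noticeably sharpen early adaptation. It would not: after the burn-in of 50 per arm, the 24 v 72 hour difference in the planning scenario is 7.5 points with a standard error of about 7.74 (survivor SD 20 assumed), or 0.97 standard errors, and at R² 10% this becomes only 1.02. The design also decides from a fitted curve and not from that contrast. A reader might also infer from 4.5 and 10.4 that allocation is biased or the error rate inflated. The protocol supports neither: randomization protects validity without stratification, and the simulated null rate is 4.6%.

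Finally, adjusting the 9.3.2 imputation adds little where a 3-month score exists. At the reported r = 0.95, that score already explains 0.95² = 90% of the 12-month variance (77% at the r = 0.88 reported for infants).

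**Conclusion.** The point holds as an inexpensive improvement of low severity. Section 9.3.1 fixes a primary model without baseline terms although suitable variables are already needed for other analyses. The loss is precision only; there is no bias, and no stated error rate or power is shown to be wrong.

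In the planning scenario the gain is about 0.4 to 2.2 power points over assumed R² of 2 to 10%, the information of about 18 to 100 extra participants. In the U-shaped scenario, where power is weakest, it is at most about 0.8 to 4.1 points. These figures rest on an R² that the protocol does not give, a normal approximation, and a one-sided reading of the 4.6%. No gain beyond R² of 10% is claimed.

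**What to change.** In 9.3.1, add a short pre-specified set of baseline terms to the mean: age group, initial GCS motor score and duration of chest compressions, each as recorded before randomization. Leave out baseline PCPC, because 6.1 reports that more than 90% of children in the earlier trial had broadly normal pre-arrest function. Report arm means standardized to the trial population, so that the duration-response curve keeps its present meaning. Use the same terms in the 9.3.2 imputation model; they matter mainly for participants without a 3-month score. Re-simulate Table 9.7.B and confirm the type I error before adopting the model. If the sponsor prefers the unadjusted model, one sentence giving the reason would close the point.

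No new visit, measurement or participant is needed, provided the case report form holds motor score and compression time as values and not only as eligibility checks; this should be confirmed first. The cost is priors for the covariate terms, a rule for missing baseline values, the simulation work, and review of a changed model that drives each 10-week look in a study under staged approval (9.12).
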